## 10. DRUG INFORMATION

### 10.1 Tremelimumab

Tremelimumab is an anti-CTLA-4 antibody being explored as a single-agent, and in combination with durvalumab, for the treatment of several malignancies.

#### 10.1.1 Supplier/How Supplied

Tremelimumab will be supplied by AstraZeneca. Tremelimumab is formulated at 20 mg/mL in 20 mM histidine/histidine-HCl, 22 mM trehalose dihydrate, 0.02% (w/v) polysorbate 80, and 0.27 mM disodium edetate dihydrate, pH 5.5. The investigational product is supplied as a sterile liquid solution containing either 400 mg (nominal) tremelimumab per vial or 25 mg (nominal) per vial. The nominal fill volume for the 400 mg presentation is 20.0 mL and the nominal fill volume for the 25 mg presentation is 1.25 mL. Investigational product vials are stored at 2°C to 8°C (36°F to 46°F) and must not be frozen. Drug product should be kept in secondary container until use to prevent excessive light exposure.

#### 10.1.2 Preparation

Total time from needle puncture of the tremelimumab vial to the start of administration should not exceed:

- 24 hours at 2°C to 8°C (36°F to 46°F)
- 4 hours at room temperature

Tremelimumab will be administered using an IV bag containing 0.9% (w/v) saline or 5% (w/v) dextrose, with a final tremelimumab concentration ranging from 0.10 to 10 mg/mL, and delivered through an IV administration set with a 0.2- or 0.22- $\mu$ m in-line filter. The IV bag size should be selected such that the final concentration is within 0.10 to 10 mg/mL. Mix the bag by gently inverting to ensure homogeneity of the dose in the bag.

Standard infusion time is 1 hour. However, if there are interruptions during infusion, the total allowed time should not exceed 8 hours at room temperature. Do not co-administer other drugs through the same infusion line.

In the event that either preparation time or infusion time exceeds the time limits a new dose must be prepared from new vials. Tremelimumab does not contain preservatives, and any unused portion must be discarded.

#### 10.1.3 Dispensing

Tremelimumab must be dispensed only from official study sites and to eligible subjects under the supervision of the site investigator. Tremelimumab should be stored in a secure area according to local regulations. It is the responsibility of the site investigator to ensure that study drug is only dispensed to subjects.

#### 10.1.4 Adverse Events

Risks with tremelimumab monotherapy include, but are not limited to, GI effects (colitis, diarrhea, enterocolitis and intestinal perforation), endocrine disorders (hypo and hyperthyroidism, hypophysitis and adrenal insufficiency), skin effects (rash, and pruritus), elevations in lipase and amylase and clinical manifestations of pancreatitis, other gastrointestinal

events e.g. ulcerative colitis, dehydration, nausea and vomiting; hepatic events including hepatitis, and liver enzyme elevations; pneumonitis and ILD; nervous system events including encephalitis, peripheral motor and sensory neuropathies, Guillain-Barre and proximal muscle weakness; cytopenias including thrombocytopenia, anemia and neutropenia; infusion-related reactions, anaphylaxis, and allergic reactions; renal events including renal failure, acute kidney injury, nephritis, nephrotic syndrome, autoimmune nephritis and electrolyte abnormalities such as hypokalemia; autoimmune diseases including autoimmune arthritis, Sjogren's syndrome and giant cell temporal arteritis; hyperglycemia and diabetes mellitus; and pyrexia. For information on all identified and potential risks with tremelimumab please always refer to the current version of the tremelimumab IB. Using pooled data from monotherapy clinical studies AEs (all grades) reported very commonly ( $\geq 10\%$  of patients) were diarrhea, nausea, fatigue, pruritus, decreased appetite, rash, vomiting, dyspnea, constipation, cough, pyrexia, abdominal pain, decreased weight, headache, asthenia, and anemia. Approximately 16% of patients experienced an AE that resulted in permanent discontinuation of tremelimumab and approximately 45% of patients experienced an SAE.

## 11 ADVERSE EVENTS

The descriptions and grading scales found in the NCI CTCAE v4.03 will be utilized for AE assessment. A copy of the CTCAE v4.03 can be downloaded from the CTEP website at <http://ctep.cancer.gov>. All forms for AE/SAE recording and reporting can be found in the Study Procedure Manual or in the EDC system (Documents and Information Tab).

### 11.1 Definitions

#### 11.1.1 Adverse Event (AE)

An AE is any untoward medical occurrence whether or not considered related to the study drug that appears to change in intensity during the course of the study. The following are examples of AEs:

- Unintended or unfavorable sign or symptom
- A disease temporally associated with participation in the protocol
- An intercurrent illness or injury that impairs the well-being of the subject

Abnormal laboratory values or diagnostic test results constitute AEs only if they induce clinical signs or symptoms or require treatment or further diagnostic tests

Hospitalization for elective surgery or routine clinical procedures that are not the result of an AE (e.g., surgical insertion of central line) should not be recorded as an AE.

Disease progression should not be recorded as an AE, unless it is attributable to the study regimen by the site investigator.

### 11.1.2 Serious Adverse Event (SAE)

A SAE is an adverse event that:

- Results in death. **NOTE:** Death due to disease progression should not be reported as a SAE, unless it is attributable by the site investigator to the study drug(s)
- Is life-threatening (defined as an event in which the subject was at risk of death at the time of the event; it does not refer to an event which hypothetically might have caused death if it were more severe)
- Requires inpatient hospitalization for >24 hours or prolongation of existing hospitalization. **NOTE:** Hospitalization for anticipated or protocol specified procedures such as administration of chemotherapy, central line insertion, metastasis interventional therapy, resection of primary tumor, or elective surgery, will not be considered serious adverse events.
- Results in persistent or significant disability/incapacity
- Is a congenital anomaly or birth defect
- Is an important medical event (defined as a medical event(s) that may not be immediately life-threatening or result in death or hospitalization but, based upon appropriate medical and scientific judgment, may jeopardize the subject or may require intervention (e.g., medical, surgical) to prevent one of the other serious outcomes listed in the definition above). Examples of such events include, but are not limited to, intensive treatment in an emergency room or at home for allergic bronchospasm; blood dyscrasias or convulsions not resulting in hospitalization; or the development of drug dependency or drug abuse.

### 11.1.3 Adverse Events of Special Interest

An adverse event of special interest (AESI) is one of scientific and medical interest specific to understanding of the study drug(s) and may require close monitoring and rapid communication by the site investigator to the sponsor-investigator. An AESI may be serious or non-serious. The rapid reporting of AESIs allows ongoing surveillance of these events in order to characterize and understand them in association with the use of the study drug(s). If any AESI occurs in the course of the study, then the site investigators or other site personnel should report to Hoosier Cancer Research Network (HCRN) **within 1 business day** of becoming aware of the event.

HCRN will report to AstraZeneca **within 1 business day** of becoming aware of the event. AESIs for tremelimumab include, but are not limited to, events with a potential inflammatory or immune-mediated mechanism and that may require more frequent monitoring and/or interventions such as steroids, immunosuppressants, and/or hormone replacement therapy. These AESIs are being closely monitored in clinical studies with tremelimumab therapy.

An imAE is defined as an AE that is associated with drug exposure and is consistent with an immune-mediated mechanism of action and where there is no clear alternate etiology. Serologic, immunologic, and histologic (biopsy) data, as appropriate, should be used to support an imAE diagnosis. Appropriate efforts should be made to rule out neoplastic, infectious, metabolic, toxin, or other etiologic causes of the imAE. In the event of imAE or suspected imAE, the sponsor-investigator may request relevant clinical information (including images) for those subjects who demonstrate the event and may request the independent review by external experts based on the acquired clinical information.

If the site investigator has any questions with regards to an AE being an imAE, the site investigator should immediately contact the sponsor-investigator.

AESIs observed with tremelimumab include the following:

- Diarrhea/Colitis and intestinal perforation
- Pneumonitis/Interstitial Lung Disease (ILD)
- Hepatitis/transaminase increases
- Neuropathy / neuromuscular toxicity (e.g. Guillain-Barré, and myasthenia gravis)
- Endocrinopathy (ie, events of hypophysitis, adrenal insufficiency, and hyperthyroidism and hypothyroidism, Type I diabetes)
- Rash/Dermatitis
- Nephritis/Blood creatinine increases
- Pancreatitis/ serum lipase and amylase increases
- Myocarditis
- Myositis/Polymyositis
- Other inflammatory responses that are rare / less frequent with a potential immune-mediated aetiology include, but are not limited to, pericarditis, sarcoidosis, uveitis and other events involving the eye, skin, haematological and rheumatological events.

In addition, infusion-related reactions and hypersensitivity/anaphylactic reactions with a different underlying pharmacological etiology are also considered AESIs. Further information on these risks (e.g. presenting symptoms) can be found in the current version of the tremelimumab Investigator's Brochure. More specific guidelines for their evaluation and treatment are described in detail in the Dosing Modification and Toxicity Management Guidelines (please see Appendix 1). These guidelines have been prepared by the Funder to assist the investigators in the exercise of his/her clinical judgment in treating these types of toxicities. These guidelines apply to AEs considered causally related to the study drug/study regimen by the reporting investigator)

#### 11.1.4 Unexpected Adverse Event

For this study, an AE is considered unexpected when it varies in nature, intensity or frequency from information provided in the current IB, prescribing information or when it is not included in the informed consent document as a potential risk. Unexpected also refers to AEs that are mentioned in the IB as occurring with a class of drugs or are anticipated from the pharmacological properties of the drug, but are not specifically mentioned as occurring with the particular drug under investigation.

#### 11.1.5 Relatedness

AEs will be categorized according to the likelihood that they are related to the study drug(s). Specifically, they will be categorized using the following terms:

|                  |  |
|------------------|--|
| Unrelated | Adverse Event is not related to the study drug(s)        |
| Unlikely  | Adverse Event is doubtfully related to the study drug(s) |
| Possible  | Adverse Event may be related to the study drug(s)        |
| Probable  | Adverse Event is likely related to the study drug(s)     |
| Definite  | Adverse Event is clearly related to the study drug(s)    |

## 11.2 Reporting

### 11.2.1 Adverse Events

AEs will be recorded from time of signed informed consent until 30 days after discontinuation of study drug(s) or until a new anti-cancer treatment starts, whichever occurs first.

- AEs will be recorded regardless of whether or not they are considered related to the study drug(s).
- All AEs will be recorded in the subject's medical record and on the appropriate study specific eCRF form within the EDC system.
- AEs considered related to study drug(s) will be followed until resolution to  $\leq$  Grade 1 or baseline, deemed clinically insignificant, and/or until a new anti-cancer treatment starts, whichever occurs first.
- Asymptomatic laboratory abnormalities that do not require treatment will not be collected as adverse events.

### 11.2.2 Serious Adverse Events (SAEs)

#### 11.2.2.1 Site Requirements for Reporting SAEs to HCRN

- SAEs will be reported from time of signed informed consent until 90 days after discontinuation of study drug(s) or until a new anti-cancer treatment starts, whichever occurs first.
- SAEs will be reported on the SAE Submission Form **within 1 business day** of discovery of the event.
- SAEs include events related and unrelated to the study drug(s).
- All SAEs will be recorded in the subject's medical record and on the appropriate study specific eCRF form within the EDC system.
- All SAEs regardless of relation to study drug will be followed until resolution to  $\leq$  Grade 1 or baseline and/or deemed clinically insignificant and/or until a new anti-cancer treatment starts, whichever occurs first.

The site will submit the completed SAE Submission Form to HCRN **within 1 business day** of discovery of the event. The form may be submitted to HCRN electronically to [[contact]](mailto:[contact]). The site investigator is responsible for informing the IRB and/or other local regulatory bodies as per local requirements.

The original copy of the SAE Submission Form and the email correspondence must be kept within the study file at the study site.

Once the SAE has resolved (see resolution guidelines listed above), sites must submit a follow-up SAE Submission Form within a reasonable timeframe to HCRN electronically to [[contact]](mailto:[contact]).

### **11.2.2.2 HCRN Requirements for Reporting SAEs to AstraZeneca**

HCRN will report all SAEs to AstraZeneca as stipulated by company **within 1 business day** of receipt of the SAE Submission Form from a site. Follow-up information will be provided to AstraZeneca as it is received from site. Send SAE report and accompanying cover page by way of email to AstraZeneca's designated mailbox: [contact]

### **11.3 Sponsor-Investigator Responsibilities**

HCRN will send a SAE summary to the sponsor-investigator **within 1 business day** of receipt of SAE Submission Form from a site. The sponsor-investigator will promptly review the SAE summary and assess for expectedness and relatedness.

### **11.4 HCRN Responsibilities to FDA**

HCRN will manage the Investigational New Drug Application (IND) associated with this protocol on behalf of the sponsor-investigator. HCRN will cross-reference this submission to the AstraZeneca's parent IND at the time of submission. Additionally, HCRN will submit a copy of these documents to AstraZeneca at the time of submission to FDA.

For protocols conducted under an IND, HCRN will be responsible for all communication with the FDA in accordance with 21CFR312 including but not limited to the 7 and 15 Day Reports, as well as an Annual Progress Report. Additionally, HCRN will submit a copy of these reports to AstraZeneca at the time of submission to FDA.

### **11.5 IND Safety Reports Unrelated to this Trial**

AstraZeneca will provide to HCRN IND safety reports from external studies that involve the study drug(s) per their guidelines. HCRN will forward safety reports to the sponsor-investigator who will review these reports and determine if revisions are needed to the protocol or consent. HCRN will forward these reports to participating sites **within 1 business day** of receiving the sponsor-investigator's review. Based on the sponsor-investigator's review, applicable changes will be made to the protocol and informed consent document (if required). All IND safety reports will also be made available to sites via the EDC system.

Upon receipt from HCRN, site investigators (or designees) are responsible for submitting these safety reports to their respective IRBs, as per their IRB policies.

### **11.6 Other events requiring reporting**

#### **11.6.1 Overdose**

Use of tremelimumab in doses in excess of that specified in the protocol is considered to be an overdose. There is currently no specific treatment in the event of overdose of tremelimumab, and possible symptoms of overdose are not established. An overdose with associated AEs will be recorded as the AE diagnosis or symptoms in the relevant eCRF.

If an overdose of a study drug(s) occurs in the course of the study, then the site investigator or other site personnel will inform HCRN **within 1 business day** of becoming aware of the event. HCRN will report the event to AstraZeneca **within 1 business day** of becoming aware of the event.

### **11.6.2 Pregnancy**

All pregnancies and outcomes of pregnancy should be reported to AstraZeneca except for:

- Pregnancy discovered before the study subject has received any study drugs.
- Pregnancy of a female partner of male subject, providing there is no restriction of male subject fathering a child.

### **11.6.3 Maternal exposure**

If a patient becomes pregnant during the course of the study, the study drug(s) should be discontinued immediately. Pregnancy itself is not regarded as an AE unless there is a suspicion that the study drug(s) may have interfered with the effectiveness of a contraceptive medication. Congenital abnormalities or birth defects and spontaneous miscarriages should be reported and handled as SAEs. Elective abortions without complications should not be handled as AEs. The outcome of all pregnancies (spontaneous miscarriage, elective termination, ectopic pregnancy, normal birth, or congenital abnormality) should be followed up and documented even if the patient was discontinued from the study.

If any pregnancy occurs in the course of the study, then the site investigator or other site personnel will inform HCRN **within 1 business day** of becoming aware of the event. HCRN will report the event to AstraZeneca **within 1 business day** of becoming aware of the event.

### **11.6.4 Paternal exposure**

Male subjects should refrain from fathering a child or donating sperm during the study and for 90 days after the last dose of tremelimumab. Pregnancy of the patient's partner is not considered to be an AE. However, the outcome of all pregnancies (spontaneous miscarriage, elective termination, ectopic pregnancy, normal birth, or congenital abnormality) occurring from the date of the first dose until 90 days after the last dose of tremelimumab therapy should, if possible, be followed up and documented.

### **11.6.5 Reporting of deaths to AstraZeneca**

All deaths that occur during the study, or within the protocol-defined 90-day post-last dose of tremelimumab safety follow-up period must be reported to AstraZeneca as follows:

- Death that is clearly the result of disease progression should be documented but should not be reported as an SAE.
- Where death is not due (or not clearly due) to progression of the disease under study, the AE causing the death must be reported to HCRN **within 24 hours** and HCRN will report to AstraZeneca as a SAE **within 24 hours**. The report should contain a comment regarding the co-involvement of progression of disease, if appropriate, and should assign main and contributory causes of death.
- Deaths with an unknown cause should always be reported as a SAE.

## 12 STATISTICAL METHODS

### 12.1 Study Design

This is a phase II trial designed to estimate the activity of single agent tremelimumab in subjects with metastatic urothelial cancer with disease progression despite prior treatment with PD-1/PD-L1 blockade. There is currently no standard treatment for such subjects. Therefore, given the durability of responses observed with immune checkpoint blockade, even a relatively low response proportion could be clinically meaningful. A Simon's 2-stage design will be applied.

### 12.2 Endpoints

#### 12.2.1 Definition of Primary Endpoint

The primary endpoint is to determine the response rate by RECIST 1.1

#### 12.2.2 Definition of Secondary Endpoints

- Safety will be determined according to the NCI Common Terminology Criteria for Adverse Events (NCI CTCAE) v4.03
- Duration of response will be the time from the first documentation of response to the time of progression as per RECIST 1.1 or death
- Progression-free survival which is defined as the time from treatment initiation to death or progression, depending on which occurs first
- Overall survival is defined as the time from treatment initiation to death

### 12.3 Sample Size and Accrual

A Simon's 2-stage design will be applied. Patients who do not receive drug or who do not complete 1 cycle of therapy for non-treatment related causes (eg, traffic accidents, trauma etc) will be replaced.

The null hypothesis that the true response rate is 2% will be tested against a one-sided alternative. In the first stage, 18 subjects will be accrued. If there are 0 responses in these 18 subjects, enrollment will be stopped. Otherwise, 10 additional subjects will be accrued for a total of 28. The null hypothesis will be rejected if 3 or more responses are observed in 28 subjects. This design yields a type I error rate of 0.02 and power of 80% when the true response rate is 15% or larger.

### 12.4 Assessment of Safety

The safety population will be defined as any patients that receive at least one dose of tremelimumab and will be used in the assessment of toxicity. Safety will be determined according to the NCI Common Terminology Criteria for Adverse Events (NCI CTCAE) v4.03. All subjects will be evaluable for adverse event evaluation from the time of their first dose of study treatment.

### 12.5 Assessment of Efficacy

All subjects who have received at least one cycle of therapy and have had their disease re-evaluated will be considered evaluable for response (exceptions will be those who exhibit objective disease progression prior to the end of Cycle 1 who will also be considered evaluable).

Patients who do not receive drug or who do not complete 1 cycle of therapy for non-treatment related causes will be replaced.

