### 9.3 Evaluation of best overall response

The best overall response is the best response recorded from the start of the treatment until disease progression/recurrence (taking as reference for PD the smallest measurements recorded since the treatment started). In general, the subject's best response assignment will depend on the achievement of both measurement and confirmation criteria.

| Target Lesions | Non-Target lesion             | New Lesion | Overall response |
|----------------|-------------------------------|------------|------------------|
| CR             | CR                            | No         | CR               |
| CR             | Non-CR/ Non-PD                | No         | PR               |
|                | Not evaluated                 | No         | PR               |
| PR             | Non-CR/ Non-PD/ not evaluated | No         | PR               |
| SD             | Non-CR/ Non-PD/ not evaluated | No         | SD               |
| PD             | Any                           | Yes or No  | PD               |
| Any            | PD*                           | Yes or No  | PD               |
| Any            | Any                           | Yes        | PD               |

\*In exceptional circumstances, unequivocal progression in non-target lesions may be accepted as disease progression.

Subjects with a global deterioration of health status requiring discontinuation of treatment without objective evidence of disease progression at that time should be classified as having “symptomatic deterioration”. Every effort should be made to document the objective progression even after discontinuation of treatment. In some circumstances it may be difficult to

distinguish residual disease from normal tissue. When the evaluation of complete response depends on this determination, it is recommended that the residual lesion be investigated (fine needle aspirate/biopsy) to confirm the complete response status.

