## 12.6 Data Analysis Plans

### 12.6.1 Analysis Plans for Primary Objective

All subjects with measurable disease who have received at least one cycle of treatment and have their disease re-evaluated will be evaluable for assessment of objective response. The objective response rates as determined by RECIST 1.1 and their associated 95% confidence intervals will be constructed based on the exact binomial test.

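### The plan does not settle whether early cancer failures count in the 18 and the 28: the evaluable-set and replacement wording lets them be left out or replaced, which would bias the response rate upward

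*Combined protocol and SAP*

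**What the plan says.** Four parts of the protocol bear on who is counted.

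- **Evaluable set, Section 12.5.** Subjects need one cycle and a disease re-evaluation, but "exceptions will be those who exhibit objective disease progression prior to the end of Cycle 1 who will also be considered evaluable".
- **Primary analysis, Section 12.6.1.** "All subjects with measurable disease who have received at least one cycle of treatment and have their disease re-evaluated will be evaluable" for objective response. The exception for Cycle 1 progression is not repeated.
- **Definition of the response rate, Section 9.4.5.** The denominator is all subjects, with no condition on cycles received or scans done.
- **Replacement.** Section 12.5 says "Patients who do not receive drug or who do not complete 1 cycle of therapy for non-treatment related causes will be replaced". Section 12.3 adds examples: those who "do not complete 1 cycle of therapy for non-treatment related causes (eg, traffic accidents, trauma etc) will be replaced". Section 5 has the same examples. None of the three says whether progression, deterioration or death from urothelial cancer is a ground for replacement.

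Two other provisions matter. Footnote 8 of the study calendar (Section 7) puts the first on-treatment scan at about 2 months. Section 9.3 says that "Subjects with a global deterioration of health status requiring discontinuation of treatment without objective evidence of disease progression at that time" are to be classed as symptomatic deterioration, but no section says that this class counts as a non-response.

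The design in Section 12.3 depends on these counts: "In the first stage, 18 subjects will be accrued", and "If there are 0 responses in these 18 subjects, enrollment will be stopped". Otherwise 10 more are accrued, and 3 or more responses in 28 reject the null.

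**The concern.** A Simon design has its stated error rates only if the subjects filling the 18 and the 28 are not selected on outcome. Here the sole test for replacement is whether the cause was related to treatment. Taken literally, death or decline from the cancer passes that test, and the patient's place goes to someone with a fresh chance to respond.

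The patient most exposed is the one who fails before any scan. With imaging at about 2 months, someone who dies or deteriorates in the first weeks has no objective progression and no re-evaluation. That patient is outside the evaluable sets of both 12.5 and 12.6.1, yet inside the all-subjects denominator of 9.4.5. If the loss falls in Cycle 1, the replacement wording is open. If it falls after Cycle 1 but before the scan, the patient is neither evaluable nor replaced.

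The thresholds are small, 0 against 1 response at stage 1 and 2 against 3 at the end, so a change of one or two patients can change the decision. Section 12.7 also allows accrual to be suspended while the 18th patient's response is awaited, and who is 18th depends on these rules. In an open-label single-arm trial that should not be a case-by-case judgement.

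**Working it through.** **Inputs from Section 12.3.** Null rate p0 = 0.02, one-sided; alternative 0.15; n1 = 18, stop at 0 responses; n = 28, reject at 3 or more. Stated type I error 0.02 and power 80%.

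**Step 1. Reproduce the design.**
P(reject | p) = Σ over x = 1 to 18 of Bin(x; 18, p) × P(X2 ≥ max(0, 3 − x)), with X2 ~ Bin(10, p).

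- At p = 0.02: 0.2554 × 0.0162 (x = 1) + 0.0443 × 0.1829 (x = 2) + 0.0052 (x ≥ 3) = 0.0174, which rounds to the printed 0.02.
- At p = 0.15: 0.1704 × 0.4557 + 0.2556 × 0.8031 + 0.5203 = 0.803, as printed.
- Chance of stopping at stage 1 under the null: 0.98^18 = 0.695.

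**Step 2. Early failures replaced.** Let q be the share of dosed patients who fail early and are swapped out, and assume that none of them would have responded. If the rate among all dosed patients is p, the rate among those counted is p/(1 − q). Filling 28 places takes 28/(1 − q) dosed patients. The values of q are assumptions; the documents give none.

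| q | Counted rate at p = 0.02 | Type I error | Stage 1 stop under null | P(reject) at all-dosed 15% | Dosed to fill 28 | 3 responses as share of dosed |
|---|---|---|---|---|---|---|
| 0 | 0.0200 | 0.0174 | 0.695 | 0.803 | 28 | 10.7% |
| 5% | 0.0211 | 0.020 | 0.682 | 0.832 | 29.5 | 10.2% |
| 10% | 0.0222 | 0.023 | 0.667 | 0.860 | 31.1 | 9.6% |
| 15% | 0.0235 | 0.027 | 0.651 | 0.886 | 32.9 | 9.1% |
| 20% | 0.0250 | 0.031 | 0.634 | 0.911 | 35.0 | 8.6% |

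The design becomes more permissive: it rejects more often at every true rate and stops less often for futility. The last column is 3(1 − q)/28.

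**Step 3. Early failures left out and not replaced.** Suppose 2 or 3 of 28 are left out, so that 26 or 25 are evaluable, with 16 of them in stage 1 and the cut-off still 3. The Step 1 formula at a 15% rate among evaluable patients gives power of 75.7% (n = 26) and 73.6% (n = 25). This loss depends on reading 15% as the rate among evaluable patients. If 15% is the rate among all dosed and those left out are all non-responders, the number of responses is unchanged and so is the power. What changes then is the estimate: 3 responses become 3/26 = 11.5% or 3/25 = 12.0% instead of 3/28 = 10.7%.

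**Step 4. After the fix.** With early failures kept as non-responders and not replaced, q = 0 and the first row applies.

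**The case against.** The case for leaving the text alone has four parts.

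1. *The accident examples show the intent.* Two of the three statements of the replacement rule cite traffic accidents and trauma, which are unconnected with the disease, and in 12.5 the rule follows a sentence making Cycle 1 progressors evaluable. A reader might infer that a Cycle 1 progressor is replaced. The documents do not say so, and on a natural reading the specific sentence governs. This stands. But the list is open-ended, 12.5 omits the examples, and the sentence protects only objective progression, not unscanned deterioration or death.
2. *Section 12.6.1 may not exclude anyone with imaged progression.* It asks that a cycle be received, not completed, and there is one infusion per cycle, on Day 1. Section 5.1.2 also provides for some patients to continue after progression. So it goes too far to say that a Cycle 1 progressor is outside the primary set; that depends on an undefined term. The need for a re-evaluation still leaves out the unscanned failure.
3. *Such cases should be few.* Objective progression in Cycle 1 needs an unscheduled scan, and entry requires ECOG 0 or 1 and a life expectancy of at least 12 weeks. This is fair for imaged progression. It limits early cancer death or decline but does not rule it out.
4. *The effect is small.* At 5% and 10%, type I error still rounds to the printed 0.02. This stands.

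A reader might also infer that early failures could be both counted and replaced, so that the cut-off of 3 is applied to 31 or 32 patients. The documents do not support that: Section 12.3 defines rejection on 28 subjects only.

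**Conclusion.** The concern holds as an unresolved conflict of wording. Sections 12.5, 12.6.1 and 9.4.5 give three descriptions of who is counted, none is tied to the 18 and the 28, and the replacement rule does not exclude disease-related loss. The clearest gap is the patient who dies of cancer or deteriorates before the first scan.

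The likely size is modest. For assumed swap-outs of 5% to 20%, type I error runs from 0.020 to 0.031 against 0.0174, and at 10% the chance of a correct futility stop falls from 0.695 to 0.667. These figures assume that every swapped-out patient is a non-responder. The power of about 74% to 76% applies only if patients are left out without replacement and 15% is the rate among those evaluable. The direction of bias in the reported rate is upward in both cases. The text should be corrected, but the design itself is sound once the counting rule is fixed.

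**What to change.** 1. Name one primary population and use it for the response rate, its confidence interval and the counts of 18 and 28. All dosed subjects, less any replaced under item 2, would fit. Align 9.4.5, 12.5 and 12.6.1 with it.
2. In Section 5, 12.3 and 12.5, limit replacement to subjects who never receive tremelimumab, or who are lost in Cycle 1 for a documented cause unrelated to both study drug and urothelial cancer.
3. State that progression, symptomatic deterioration or cancer death before re-evaluation counts as a non-response and is not a ground for replacement.
4. Carry the 12.5 exception for Cycle 1 progression into 12.6.1.

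The cost is an amendment of wording. The sample size and cut-offs stay as they are, and fewer replacement patients are needed. The reported response rate may be slightly lower. If the sponsor already intends to count this way, the change only records it.
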